2. OBJECTIVES

2.1. Primary objective:

- To describe the clinical management in asthmatic patients in the influential area of Hospital Universitario Virgen de la Victoria according to the assistant quality indicators established by GEMA guidelines (Appendix 1), which are the following:
 - Diagnostic confirmation by spirometry with test bronchodilator. The diagnostic confirmation of the patients with asthma is done with spirometry and bronchodilator test as an objective measure of functional impairment.
 - Sensitization study in allergic asthma. To patients with suspicion of allergic asthma should be performed a study of possible sensitization to different allergens.
 - Smoking cessation. It is recommended smoking cessation to smokers with asthma.
 - Educational plan in patients with asthma. Patients with asthma must follow a basic education program (formed by: knowledge about their illness, about their treatment, action plan and inhalation technique, documented in writing) as part of their treatment.
 - Treatment of choice in persistent asthma. The treatment of choice in persistent asthma includes inhaled glucocorticoid (IGC) used daily. In some justified cases, alternative treatment with leukotriene receptor antagonists can be considered.
 - Asthma treatment in pregnant women. In asthma maintenance treatment in pregnant woman is recommended to keep the commonly used drugs (agonists β_2 -adrenergic and inhaled glucocorticoids).
 - Periodic follow-up of patients. Necessity to make periodic monitoring of patients, even if they have not suffered exacerbations, through scheduled medical visits.

- Periodic record of exacerbations. The specific assessment of exacerbations is evaluated periodically.

2.2. Secondary objectives:

- To describe the sociodemographic and clinical characteristics of the study population.
- To describe the treatment patterns (maintenance treatment, reliever treatment, type of treatment) during the last year.
- To describe the disease control level in the study population.
- To describe the use of resources (emergency visit, Primary care visits, specialist visits) during the last year.
- To describe the number of patients with discontinuation of SABA within the last year and the potential impact on disease control level and use of resources.

For descriptive purposes, an analysis of the objectives will be made based on the level of disease control.

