3. RESEARCH METHODOLOGY

3.1. Study Design

A non-Interventional, descriptive, cross-sectional and unicentric study, has been designed and will be conducted in a Spanish hospital of Málaga. The design of the study imposes an only visit to be performed to obtain the patient's signed IC and after signing it (if patient agreed to participate in the study), to perform an Asthma Control Test (ACT) (Appendix 2). Except for this study visit, the rest of study will be based on electronic medical chart review of approximately 300 asthma patients belonging the influential area of Hospital Universitario Virgen de la Victoria. This chart review will be performed by the site investigator or collaborators.

The data collection is stated in 6 months, and during this period the investigators will identify and randomly include the patients who meet selection criteria to avoid bias during patient's

inclusion. The observational period will be conformed of 12 months, and the patient's data will be collected or documented in an electronic case report form (eCRF), which will automatically create or assign an identification numerical code to every patient the moment it's created in the electronic platform. This system guarantees the anonymization of each patient included in the study as no identifiable information won't be able to be captured.

[figure not shown]

Figure 1. Overall Study design

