3.3.1.2. Secondary Endpoint(s)

- Demographic characteristics.
 - Age
 - Gender: male, female.
 - Ethnicity: Caucasian / Hispanic / African / Asian / Other / Unknown
 - Weight (kg) and height (cm): BMI autocalculated by the eCRF.
 - Pregnancy status (yes/no)
 - Smoking status (current smoker, ex-smoker*, non-smoker)
- **It will be considered that the patient is ex-smoker since the 6 months of non-smoking.*
- Clinical characteristics:
 - Age at asthma diagnosis
 - Spirometry and bronchodilator test at diagnose
 - Patient's derivation: primary care / specialized healthcare

- Asthma severity degree according to GEMA guidelines: Mild intermittent, Mild persistent, Moderate persistent and Severe persistent.
- Asthma disease control level according to:
 - Clinical criteria (number of SABA canisters retired from the pharmacy in the previous year, number of OCS retired from the pharmacy in the previous year, number of emergency service visits in the previous year, number of unscheduled primary care visits in the previous year).
 - Asthma Control Test (ACT) (most recent value available): No / Yes, specify score: ACT \geq 20 points (controlled) / ACT less than 20 uncontrolled.
- History of allergic asthma (or suspected): No / Yes.
- Sensitization to allergen study (for those patients with a diagnosed history of suspected allergic asthma).
- Registration of asthma education programs performed (last asthma education program performed by the patient): year when it was performed.
- Current asthma therapeutic level according to GEMA stepwise therapy (at patient's inclusion date): Step 1 / Step 2 / Step 3 / Step 4 / Step 5 / Step 6.
- Comorbidities (at patient's inclusion date) according to Charlson Comorbidity Index (autocalculated). A list of diseases will be displayed in order to be selected those the patient suffers at the inclusion date. The Charlson Comorbidity index score will be autocalculated automatically by the eCRF.
- Maintenance/long-term and reliever treatment prescribed for asthma (at inclusion date): type (SABA, LABA, GCI, LTRA, Biologic, immunomodulator, others), initiation date, end date or if its ongoing. Maintenance/long-term and reliever treatment prescribed for asthma in pregnant women (at inclusion date): type (SABA, LABA, GCI, LTRA,

Biologic, immunomodulator, others), initiation date and end date or if its ongoing.

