- To describe the disease control level in the study population. A descriptive analysis will be performed of the disease control level.
- Use of assistance health resources (secondary objective 3): resource use will be evaluated as number of visits performed by the patient the prior year to the inclusion date:
 - Emergency department (ED) linked to asthma.
 - Hospitalizations linked to asthma.
 - Primary care visits (scheduled and unexpected) linked to asthma.
 - Specialist visits (allergists, pulmonologists, etc.) linked to asthma.
- To describe the number of patients with discontinuation of SABA within the last year: It will be described the number of patients with SABA discontinuation during the prior year of the study inclusion date.
-

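### Objective 5 relates SABA discontinuation to a control level that partly counts SABA canisters from the same year, so part of any association is built in

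*Combined protocol and SAP*

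**What the plan says.** Section 2.2 and the synopsis set as the last secondary objective the number of patients with "discontinuation of SABA within the last year and the potential impact on disease control level and use of resources". Section 2.2 closes by adding that "an analysis of the objectives will be made based on the level of disease control".

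Section 3.3.1.2 measures control level in two ways:

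- Clinical criteria, beginning "Clinical criteria (number of SABA canisters retired from the pharmacy in the previous year", followed by OCS collected from the pharmacy, then "number of emergency service visits in the previous year, number of unscheduled primary care visits in the previous year". No cut-off is given for any of the four, and no rule for combining them.
- ACT, with a threshold of 20: "points (controlled) / ACT less than 20 uncontrolled".

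Nothing says which of the two defines control level if they disagree, or which one serves objective 5.

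On analysis, Section 4 says of control only that "A descriptive analysis will be performed of the disease control level". On stopping SABA it says "It will be described the number of patients with SABA discontinuation during the prior year of the study inclusion date". Discontinuation itself is not defined.

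**The concern.** The exposure in objective 5 and one component of the outcome both come from SABA use in the same 12 months. A patient who stops part-way through the year collects no more canisters after that date, whether the asthma is better, worse or unchanged. On that one criterion, stopping can only leave the patient's status as it was or improve it.

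If the clinical criteria serve as the control level, a table of control by discontinuation, or of discontinuation by control level, mixes two things: any real relation between stopping and control, and an effect of how control was scored. The objective speaks of impact, so a report that follows it could present the scoring effect as a finding about stopping SABA.

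**Working it through.** **No figure in the plan to reproduce on this point.** The documents give no expected rate of discontinuation, no canister distribution and no proportion controlled. The one sample-size figure is for a single proportion of 50% ± 6 points: 1.96² × 0.25 / 0.06² = 266.8, so 267, as stated in Section 3.4. It does not depend on this point.

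**What the text leads to.** The objective asks about discontinuation and control level. The closing sentence of Section 2.2 splits every objective by control level. One of the two measures of control level contains the canister count for the same look-back year. No sentence takes the count out for objective 5.

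**Size and direction.** The following is an illustration with no true effect of stopping. All inputs are assumptions:

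- Continuers collect canisters as a Poisson count with mean r = 2, 3 or 4 a year.
- Stoppers collected at rate k × r until stopping (k = 1, 2 or 3) and none afterwards. Stop dates are uniform over the year.
- A patient fails the canister criterion at c = 2, 3 or 4 or more canisters.
- A patient is controlled only if no criterion fails. The other three fail with probability q = 0 or 0.3, independently and equally in both groups.

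Mean canisters are r in continuers and k × r / 2 in stoppers. Stoppers therefore average half the continuers' count at k = 1, the same at k = 2, and 1.5 times at k = 3.

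With F the Poisson distribution function, the proportion controlled is:

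- continuers: (1 − q) × F(c − 1; r)
- stoppers: (1 − q) × [1/(kr)] × Σ from j = 0 to c − 1 of [1 − F(j; kr)], the average over stop dates

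For r = 3, c = 3, q = 0:

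- continuers: e⁻³ × (1 + 3 + 4.5) = 0.423
- stoppers, k = 1: (0.950 + 0.801 + 0.577) / 3 = 0.776
- stoppers, k = 2: 2.918 / 6 = 0.486
- stoppers, k = 3: 2.992 / 9 = 0.332

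| Stoppers' earlier rate relative to continuers | Difference at r = 3, c = 3, q = 0 | Range over all r, c, q |
|---|---|---|
| Equal (k = 1) | +35.3 points | +7.4 to +42.5 |
| Twice (k = 2) | +6.3 points | -5.2 to +15.8 |
| Three times (k = 3) | -9.1 points | -22.9 to +7.5 |

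Differences are stoppers minus continuers in proportion controlled. Every one arises with no change in disease. The sign depends on earlier use and on a cut-off that the protocol does not state.

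**With ACT as the measure.** As written in Section 3.3.1.2, the canister count is not an input to the ACT classification, so this source of built-in difference drops out.

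**The case against.** The strongest reply is that the circular comparison is not a planned analysis. Section 4 plans a count of patients who discontinued, describes variables separately, and defers interpretation to a later SAP. Section 3.5 disclaims hypothesis testing. This is true, and it limits the point: the link comes from the wording of the objective and the general breakdown by control level. But both are stated aims. Unless the measure is settled, either the second half of objective 5 goes unanswered or the choice is made later without guidance. A purely descriptive table would carry the same artefact.

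A reader might infer more: that discontinuation and control are the same quantity, so that stopping SABA improves control by arithmetic and stoppers must look better. The documents do not support this. Canisters are one of four clinical criteria, with no cut-off or combining rule. ACT is a separate measure with its own threshold. Section 3.3.1.2 records treatments with start and end dates, and nothing says that discontinuation is derived from the canister count. The 12-month count also includes canisters collected before stopping, so heavier earlier users who stop may still count as uncontrolled.

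It is also fair to object that ACT is not a ready-made answer. Section 3.1 has the study visit used "to perform an Asthma Control Test (ACT) (Appendix 2", but Section 3.3.1.2 takes the latest ACT value on file and allows for there being none, and Section 3.3 says all study data come from the chart. Appendix 2 is only a link, so the documents do not show whether any ACT item concerns reliever use. These points stand and shape the fix.

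**Conclusion.** The point holds in a limited form. On the clinical criteria, part of any association between SABA discontinuation and control level is built in, because the canister count for the same year is one component. The within-patient direction on that component is fixed; the direction between patients is not. The artefact has unknown sign and, under the assumed inputs, ranges from -22.9 to +42.5 points. It therefore cannot be corrected afterwards by assuming that stoppers are flattered, and the result cannot be read as an impact of stopping.

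The range rests on the assumed Poisson counts, cut-offs, uniform stop dates and scoring rule; the overlap itself rests only on the text. It affects one secondary objective of a descriptive study. The primary endpoint and the sample size are untouched.

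**What to change.** In Section 2.2 and Section 4, and in the SAP to be agreed:

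1. State that for objective 5, including its breakdown by control level, control is measured by ACT at the study visit (score, and 20 or more against below 20).
2. Give the clinical criteria without the canister count as a supporting description, with their cut-offs and combining rule. OCS, emergency and unscheduled primary care visits need not be discarded. Note that the two visit counts are also resource-use outcomes, so in objective 5 they are not separate evidence.
3. Report canisters only as a descriptor of SABA use.
4. Reconcile Section 3.1, Section 3.3 and Section 3.3.1.2 on whether ACT is the visit value or the latest value in the chart, and check whether any ACT item concerns reliever use.
5. Define SABA discontinuation from the recorded treatment end date. The treatment field is labelled as at inclusion, so confirm that the eCRF also captures SABA that ended during the look-back year.
6. Describe the result as an association. Even with ACT, poor or good control earlier in the year may have led to the stopping.

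The cost is a few sentences and one check of the eCRF. The downside is that control for objective 5 rests on fewer components. No patients are added.

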	
 • Sensitization study in allergic asthma. To patients with suspicion of allergic asthma should be performed a study of possible sensitization to different allergens. • Smoking cessation. It is recommended smoking cessation to smokers with asthma. • Educational plan in patients with asthma. Patients with asthma must follow a basic education program (formed by: knowledge about their illness, about their treatment, action plan and inhalation technique, documented in writing) as part of their treatment. • Treatment of choice in persistent asthma. The treatment of choice in persistent asthma includes inhaled glucocorticoid (IGC) used daily. In some justified cases, alternative treatment with leukotriene receptor antagonists can be considered. • Asthma treatment in pregnant women. In asthma maintenance treatment in pregnant woman is recommended to keep the commonly used drugs (agonists β2-adrenergic and inhaled glucocorticoids). • Periodic follow-up of patients. Necessity to make periodic monitoring of patients, even if they have not suffered exacerbations, through scheduled medical visits. • Periodic record of exacerbations. The specific assessment of exacerbations is evaluated periodically. 
Secondary objectives:
 
 1. To describe the sociodemographic and clinical characteristics of the study population. 2. To describe the treatment patterns (maintenance treatment, reliever treatment, type of treatment) during the last year. 3. To describe the disease control level in the study population. 4. To describe the use of resources (emergency visit, Primary care visits, specialist visits) during the last year. 5. To describe the number of patients with discontinuation of SABA within the last year and the potential impact on disease control level and use of resources. 
For descriptive purposes, an analysis of the objectives will be made based on the

--	--

	level of disease control.
Study Design	Cross-sectional cohort, non-interventional, descriptive and unicentric
Study Population and Sampling Methods	
It is planned that a total of 300 patients with asthma will be included in the study.
 
 - Target enrollment/ sample size: 300 patients approximately. - Anticipated rate of enrollment: 6 months. - Estimated study start date: September - Estimated study completion date: March
Data Source	Patient's electronical medical chart

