- Record of scheduled monitoring asthma visits in the last year (the year prior since the patient's inclusion date): register confirmation and number of scheduled visits performed.
- History of asthma exacerbations during the last year (the year prior since the patient's inclusion date): register confirmation and number of asthma exacerbations.
- Use of health resources during the last year (the year prior since the patient's inclusion date): visits to emergency department (ED), visits to primary health care department, visits to specialist.
 - Nº of emergency department (ED) and hospitalization visits related to an asthma diagnosis code in the last year since the date of study inclusion.
 - Treatment prescribed at discharge: type (SABA, OCS, LABA, GCI, LTRA, Biologic, immunomodulator, others).
 - Nº of primary health care department visits related to an asthma diagnosis performed during the last year since the date of study inclusion (scheduled and unexpected),
 - Nº of specialist (allergology, physiotherapy, others) visits related to an asthma diagnosis performed during the last year since the date of study inclusion.
- Nº of oral corticosteroids (OCS) prescriptions in the last year (prior year since the patient's inclusion date).

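### Does leaving the disease-control grouping unnamed make the resource-use tables circular?

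*Combined protocol and SAP*

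**What the plan says.** Section 3.3.1.2 describes disease control in two ways.

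- **Counts.** The entry opens with "Clinical criteria (number of SABA canisters retired from the pharmacy in the previous year", adds oral corticosteroids collected from the pharmacy, and ends with "number of emergency service visits in the previous year, number of unscheduled primary care visits in the previous year". No threshold is given for any count and no rule combines them.
- **ACT.** The entry reads "Asthma Control Test (ACT) (most recent value available" and then sets 20 points or more as controlled and less than 20 as uncontrolled. Section 3.1 has the ACT performed at the single study visit, after consent.

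Section 2.2 closes by saying that, for descriptive purposes, "an analysis of the objectives will be made based on the level of disease control"; the synopsis says the same. Neither names the grouping variable, and Section 4 says only that control level will be described.

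The resource-use outcomes, also in Section 3.3.1.2, include "emergency department (ED) and hospitalization visits related to an asthma diagnosis code in the last year" and asthma-related primary care visits "performed during the last year since the date of study inclusion (scheduled and unexpected". Section 4 takes them over the year before inclusion. The last secondary objective concerns "discontinuation of SABA within the last year and the potential impact on disease control level and use of resources".

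Section 4 describes all variables separately and requires a statistical analysis plan to be agreed before analysis begins. Section 3.5 states that no hypothesis is tested.

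**The concern.** Two of the four counts listed under control, emergency visits and unscheduled primary care visits, reappear as resource-use outcomes over the same twelve months. If patients were called uncontrolled because they had such visits, a table of visits by control level would show an excess in the uncontrolled group even where visits and control were unrelated. A reader could not separate that built-in part from a real difference.

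The last secondary objective has a similar weakness. SABA canisters are one of the counts, so a count-based control level would not be independent of SABA discontinuation.

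Because the protocol promises an analysis by control level and names no grouping variable, it does not expressly rule this out. The study aims to find ways of improving asthma control, so a difference made by the definition could be read as a burden of poor control.

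**Working it through.** The plan states no figure for this comparison. The first check is therefore a reading of the text, followed by a calculation of what would happen under the grouping that the text does not specify.

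**1. Which definition can classify a patient?**

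| Item in Section 3.3.1.2 | Cut-off given | Controlled/uncontrolled label | Combining rule |
|---|---|---|---|
| SABA canisters collected | no | no | no |
| Oral corticosteroids collected | no | no | no |
| Emergency visits | no | no | no |
| Unscheduled primary care visits | no | no | no |
| ACT | yes, 20 | yes | not needed |

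Only the ACT yields groups without a further rule being invented. Describing variables separately, as Section 4 provides, fits reporting the four counts one by one.

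**2. Does ACT grouping build in an overlap?** The groups are formed from the ACT score and no visit count enters the rule. If visits are unrelated to ACT status, the expected means are equal. A simulation of 2,000,000 patients with visits independent of ACT gave 0.50 against 0.50 emergency visits and 1.00 against 1.00 primary care visits, at assumed means of 0.5 and 1.0.

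**3. What if a count-based level were used?** Let X be the yearly visits, Poisson with mean m. Call a patient uncontrolled if X ≥ c or if an independent criterion, with probability p, is met. Then

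- controlled mean = E[X; X < c] / P(X < c)
- controlled share = P(X < c) × (1 − p)
- uncontrolled mean = (m − controlled mean × controlled share) / (1 − controlled share)

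The values of m, c and p are all assumptions, because the documents give none.

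*Large case:* m = 0.5, c = 2, p = 0.10.
- P(X < 2) = 0.9098 and E[X; X < 2] = 0.3033, so the controlled mean is 0.3033 / 0.9098 = 0.333.
- Controlled share = 0.9098 × 0.90 = 0.8188.
- Uncontrolled mean = (0.5 − 0.3333 × 0.8188) / 0.1812 = 1.253.
- Difference 0.92 visits, ratio 3.8.

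*Small case:* m = 0.1, c = 3, p = 0.50.
- Controlled mean 0.0995, uncontrolled mean 0.1005.
- Difference 0.001 visits, ratio 1.01.

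With c = 1 the controlled mean for emergency visits is 0 by construction. For unscheduled primary care visits at m = 0.5 and p = 0.50, moving the cut-off from 2 to 3 lowers the ratio from 1.92 (0.639 against 0.333) to 1.16 (0.537 against 0.462).

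The built-in part therefore depends almost wholly on a rule that the protocol does not contain.

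**4. How close is the overlap?** It is partial even then. The resource-use outcomes are restricted to asthma-linked visits, while the counts under control are not. The emergency item in Section 3.3.1.2 also includes hospitalizations, and the primary care outcome also includes scheduled visits.

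**5. What else depends on it?** The sample size rests on one proportion: 1.96² × 0.25 / 0.06² = 266.8, rounded up to 267, with 300 planned after the allowance for unavailable data. No control grouping enters. Nor does one enter the overall calculation of any of the eight GEMA indicators in Section 4.

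**The case for a change.** The strongest case for a change is that the protocol places the four counts under control level, ahead of the ACT, and so appears to contemplate classifying by them. The ACT source is also not fully settled. Section 3.1 has it done at the visit, Section 3.3.1.2 takes the latest available value and allows for none, and Section 3.3 says all data come from source documents. A patient without an ACT might then be classified from the counts. Nothing commits the later analysis plan to a grouping variable, and naming one would cost a sentence.

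Part of this stands: the grouping variable is unnamed, and a count-based level would create the overlap described. The rest carries less weight. An ACT done at the study visit would ordinarily be the latest value available, and recording it in the chart would satisfy Section 3.3. No text says that a missing ACT is to be replaced by the counts. Choosing the stratifier for descriptive tables is ordinary content for an analysis plan, which here must be agreed before analysis.

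On SABA discontinuation, Section 4 plans only the number of patients who discontinued and specifies no table by control level, so no planned table there is shown to be affected.

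**Conclusion.** The concern does not call for a change. The harm requires a composite control level that the protocol does not define; the grouping it can carry out as written, ACT at 20, has no built-in overlap with visits. The gap is a missing detail that analysts would settle sensibly in the analysis plan, by grouping on the ACT and reporting the four counts as separate variables.

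At most, some secondary descriptive tables of resource use would be affected, and only if a count-based level were used. The size of that effect cannot be derived from the documents. In the assumed emergency-visit scenarios with cut-offs of 2 or 3, the ratio runs from 1.01 to 3.8, which is no evidence about this study.

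The conclusion rests on two assumptions: that the ACT is obtained at the study visit as Section 3.1 provides, and that the analysis plan is agreed before analysis as Section 4 requires. If that plan did adopt a count-based level, its tables of emergency and unscheduled primary care visits could not be read as independent evidence of the burden of poor control.
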